Outcome Measures: The first four items of the Brief Pain Inventory were collected daily: worst, average, least, and current surgical pain measured using the Numeric Rating Scale (provided verbally to the investigator with specificity to the 0.1 unit). The primary outcome measure was “average” pain score on the first 2 postoperative days. Additional outcomes included daily opioid use, sleep disturbances due to pain (binary), opioid and local anesthetic infusion (e.g. perioral numbness) side effects (binary), local anesthetic leakage (binary), complete catheter dislodgement (binary), degree of sensory block (measured on a 0-10 scale with 0: no deficits and 10: completely insensate), satisfaction with postoperative analgesia (0: very dissatisfied, 10: completely satisfied), and the volume of local anesthetic consumed.

Statistical methods: We assessed the balance of randomized groups on baseline and procedural characteristics using absolute standardized difference, defined as the absolute difference in

means, mean ranks, or proportions divided by the pooled standard deviation. Baseline variables with Absolute Standardized Difference > 0.46 (i.e., $1.96 \times \sqrt{(1/n_1 + 1/n_2)}$) were considered imbalanced and were adjusted for in all analyses, as appropriate.⁹ All analyses used modified intention-to-treat such that all patients randomized and receiving at least some of the study intervention were included.

We tested noninferiority of the suture method to the through-the-needle perineural catheter method on the primary outcome of average pain score and other continuous secondary outcomes in the first 2 days after surgery using a 1-tailed noninferiority t-test at the 0.025 significance level. We used an *a priori* noninferiority delta of 1.25 for each pain score outcome and a ratio of means of 1.2 for the cumulative log-transformed opioid consumption. Noninferiority was claimed if the upper 95% confidence limit for the treatment effect (estimated from analyses described below) was less than the specified noninferiority delta. P-values were obtained from a 1-tailed t-test using a test statistic defined as $T_{NI} = (\hat{\beta} - \delta) / SE(\hat{\beta})$, where $\hat{\beta}$ is the estimated treatment effect, $SE(\hat{\beta})$ is the estimated standard error of the treatment effect, and δ is the noninferiority delta. If noninferiority was found, superiority would be tested in the same direction.

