We assessed the effect of suture-method to the through-the-needle perineural catheter on each of 4 pain scores in the first 2 postoperative days using a repeated measures linear mixed effects model with an unstructured within-subject correlation structure adjusted for a variable's imbalances at baseline (age was the only imbalanced variable). The heterogeneity of the estimated treatment effect over time was assessed *via* the treatment-by-time interaction at a

significance criterion of $P < 0.15$. A significant interaction suggested that the treatment effect varies over time, in which case we estimated the treatment effect individually for each of 2 time points at the 0.0125 significance level using Bonferroni correction ($0.025/2$). Treatment effect estimates from these regression models were used to assess noninferiority of the suture versus through-the-needle methods, as described in the preceding paragraph.

For cumulative opioid consumption during the first 2 days after surgery, we first estimated the treatment effect of the suture method versus the through-the-needle method on log-transformed opioid consumption using linear regression and adjusting for age. If a patient did not receive opioids (amount = 0), 0.5 mg was added in order to facilitate the log-transformation.

We originally planned to estimate the effect of the treatment on the side effect of complete catheter dislodgment as a secondary outcome for testing noninferiority. However, we observed no event in the suture method group. Therefore, we simply compared the groups using Fisher's exact test. We also compared the randomized groups on binary outcomes using chi-square or Fisher's exact test, as appropriate.

Sample size and power estimation: The study was designed to have 90% power at the 0.025 significance level to detect noninferiority of the suture method to the through-the-needle perineural catheter on mean "average" pain score on the first 2 days following foot/ankle surgery. Assuming a noninferiority delta of 1.25 points, a standard deviation of 2.2, and a true difference of 0.5 points in the pain score favoring the suture method, a total sample size of 70

patients (35 per group) was required. SAS statistical software (Carey, NC) was used for all analyses.

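### A treatment-by-time pretest at P < 0.15 chooses the primary noninferiority test, and the Bonferroni split does not cover that choice, so the stated one-sided 0.025 is modestly exceeded

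*Combined protocol and SAP*

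**What the plan says.** Outcome Measures names the Brief Pain Inventory average item as primary: the "pain score on the first 2 postoperative days". Statistical methods tests noninferiority "using a 1-tailed noninferiority t-test at the 0.025 significance level", with a margin of 1.25 points, and gives the decision rule: "Noninferiority was claimed if the upper 95% confidence limit for the treatment effect" lies below the margin. It continues: "If noninferiority was found, superiority would be tested in the same direction".

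The repeated-measures paragraph then tests the treatment-by-time interaction at P < 0.15. It explains that "A significant interaction suggested that the treatment effect varies over time", and in that case "we estimated the treatment effect individually for each of 2 time points at the 0.0125 significance level using Bonferroni correction", that is, 0.025/2 per day. The paragraph closes: "Treatment effect estimates from these regression models were used to assess noninferiority", referring back to the rule above.

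Sample size and power estimation refers to a single test: "The study was designed to have 90% power at the 0.025 significance level to detect noninferiority", on the mean score over the first 2 days, with 35 patients per group.

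**The concern.** Two different tests can carry the primary claim, and a pretest on the same data chooses between them. Halving alpha protects against testing two days. It does not protect against switching to the day tests precisely when the two days look different, which is also when one day is more likely to look favorable by chance.

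The text also leaves the conclusion partly open. It does not say that the day-specific effects replace the two-day effect, that each day then gets its own verdict, or what opens the superiority step when only one day passes. The same gap applies to each of the four pain scores. At stake are the stated 0.025 error rate and a reader's ability to tell which claim the trial was entitled to make.

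**Working it through.** **Inputs from the documents.** Margin 1.25; SD 2.2; true difference 0.5 favoring suture (-0.5); 35 per group; one-sided 0.025; interaction P < 0.15; 0.0125 per day.

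**Assumed.** Between-day correlation ρ of 0.3, 0.5, 0.7 or 0.9; equal SD on both days; complete data. The documents do not say whether 2.2 is the SD of the two-day mean or of one day, so both are shown where it matters. SD of the mean = daily SD × √((1+ρ)/2), so an SD of 2.2 for the mean implies a daily SD of 2.73/2.54/2.39/2.26.

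**1. The plan's own figure.** The distance from the true effect to the margin is 1.25 + 0.5 = 1.75.
- Normal approximation: n = 2 × 2.2² × (1.960 + 1.282)² / 1.75² = 33.2, so 34 per group.
- Noncentral t at 35 per group: SE = 2.2 × √(2/35) = 0.526; 1.75/0.526 = 3.33; power 0.907. At 34 per group it is 0.898.

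So 35 per group is correct for the single two-day test. If 2.2 is the daily SD, that test has power 0.98/0.97/0.94/0.92.

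**2. Simulated rule.** Bivariate normal day differences with estimated variances and 68 df. If the interaction has two-sided P < 0.15, each day is tested with critical t 2.292; otherwise the two-day mean is tested with critical t 1.995. There were 1,000,000 trials per scenario, except 400,000 for step 5.

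**3. Both days at 1.25 (every noninferiority claim is false).**

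| ρ | 0.3 | 0.5 | 0.7 | 0.9 |
|---|---|---|---|---|
| Branch entered | 0.150 | 0.150 | 0.150 | 0.150 |
| Undiverted trials, 0.85 × 0.025 | 0.021 | 0.021 | 0.021 | 0.021 |
| At least one day passes, in the branch | 0.0134 | 0.0106 | 0.0078 | 0.0046 |
| At least one false claim | 0.035 | 0.032 | 0.029 | 0.026 |

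If the choice of branch were unrelated to the day tests, the branch could add at most 0.15 × 0.025 = 0.004 and the total would stay within 0.025. It adds more because a large gap between days and a low estimate on one day occur together. At ρ = 0.3, the false-claim rate within the branch is 0.0134/0.150 = 0.09.

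**4. How often exactly one day passes (share of all trials).**
- Planned effect, -0.5 on both days: 11/9/6/3% (SD of the mean) or 8/7/5/3% (daily SD).
- Illustrative effects -1.0 and 0, same average: 36/40/44/45% (SD of the mean) or 35/38/41/44% (daily SD).

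**5. Would stating a rule for the branch repair it?**
- Separate claims by day: no. With both days at 1.25, every claim is false whatever its label, so the error stays at 0.026 to 0.035.
- Both days required: the error is 0.021 to 0.022 with both days at 1.25. With true effects 1.25 and 0, however, trials that do not enter the branch can still claim on the two-day test. For the hypothesis that both days are noninferior, false claims are then about 0.09/0.06/0.03/0.01 (SD of the mean).

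**6. Fixed two-day test.** Error is 0.025 with the two-day mean at the margin; power is as in step 1.

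**The case against.** The strongest reply is that the text nearly supplies the rule. The noninferiority rule applies to the effect estimated in the analyses that follow, and those analyses replace one effect by two when the interaction is positive. Splitting 0.025 in two fits a separate conclusion for each day, so a one-day pass would mean noninferior on that day. This is the most natural reading. It reduces the gap to an unstated label and an unstated trigger for superiority, but it does not bring the error back to 0.025 (working, step 5).

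It is also fair that the primary outcome's average is the questionnaire item and not explicitly an average over days. A two-day contrast is a reasonable reading, consistent with the power statement, but it is not defined in those terms.

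Four stronger inferences are tempting and not supported:
- *The reported result is compromised.* The documents do not say whether the branch was entered.
- *The sample size is wrong.* It is right for the two-day test. A loss of power arises only if both days must pass, which the documents never require.
- *The plan leaves over a third of trials without a conclusion.* That figure needs invented, unequal day effects; under the planned effect it is 3 to 11%.
- *The confidence limit is wrong.* A one-sided 0.0125 test matches a two-sided 97.5% limit while the rule names only 95%, but the 0.0125 level is stated, so this is a wording point.

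**Conclusion.** The concern holds in a limited form. The interaction pretest lets the data choose the primary test, and the Bonferroni split leaves that choice uncontrolled. With both days at the margin, the chance of at least one false claim is 0.026 to 0.035 instead of 0.025. The excess is 0.01 at most over the correlations examined and nearly vanishes at 0.9. It rests on a correlation that the documents do not give, on equal SDs and on complete data; it does not depend on how the SD of 2.2 is read. The unstated trigger for superiority after a one-day pass is a real but smaller gap. Correction is worthwhile because the remedy is cheap and matches the test that was powered. If the branch was not entered, the reported primary result is unaffected.

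**What to change.** In the repeated-measures paragraph of Statistical methods, make the mixed-model treatment difference averaged over days 1 and 2 the sole primary noninferiority test at one-sided 0.025 (upper limit of the two-sided 95% interval below 1.25), whatever the interaction shows. Let the same contrast open superiority. Report the interaction and the day-specific differences with confidence intervals as supportive. Do not keep the branch and merely add a rule for it, since neither rule in step 5 of the working repairs it.

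The text is written after the fact (it already reports that age was the only imbalanced variable). The report should therefore disclose which branch was taken and that this contrast was fixed afterwards.

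The cost is one contrast from the same model, with no new data and no change to the 70 patients. The downside is that the average can pass when one day does not; the day-specific intervals make that visible.

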If a postoperative neurologic exam was desired by the surgeon, no local anesthetic was administered pre-operatively. In cases where no post-operative exam was anticipated, 20 mL 2% lidocaine with 5-10 µg/mL epinephrine was injected *via* the catheter immediately following placement. This was done under ultrasound visualization to confirm that the injection produced circumferential spread of the LA around the sciatic nerve. Successful block was defined as a decrease in temperature discrimination to ice after 30 minutes in the tibial nerve distribution. For cases in which the surgeon desired a postoperative exam prior to local anesthetic administration, a bolus with the same lidocaine-epinephrine volume/concentration was performed in the post-anesthesia care unit.

If the planned surgical procedure was anticipated to produce pain in the saphenous nerve distribution, a single-injection saphenous nerve block was performed with 20 mL 0.5% ropivacaine with 5-10 µg/mL epinephrine administered *via* a 17-gauge Tuohy needle under direct ultrasound visualization.

Intra-operative Procedures: Surgical anesthesia was provided with either pre-operative administration of local anesthesia as part of the nerve block combined with propofol sedation, or general anesthesia consisting of inhaled volatile anesthetic with or without nitrous oxide in oxygen with opioids provided, as needed.

Post-operative Procedures: Subjects received a 3-day perineural infusion via electronic pump (ambIT® PreSet, Summit Medical Products Inc, Salt Lake City, UT) of ropivacaine 0.2% (basal

6 mL/hour; 4 mL demand bolus; 30-minute lockout) initiated in the recovery room along with a prescription for oxycodone 5 mg tablets prior to discharge for supplementary analgesia. Subjects were contacted by telephone for 4 days following surgery to collect study outcome measures.

On the third postoperative day, subjects or their caretakers were instructed to remove the perineural catheter. Subjects were instructed to remove the occlusive dressing at the skin entry site and slowly pull out the catheter. Subjects in the suture-catheter group were specifically instructed to leave the distal dressing in place until the catheter was completely removed, thus ensuring that the small tail at the exit site was pulled through the skin prior to sterile dressing removal to avoid contamination of the catheter track.

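### Zero opioid use is set to 0.5 mg before the log and no alternative is checked, so if there are zero users the secondary opioid noninferiority result can depend on that constant

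*Combined protocol and SAP*

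**What the plan says.** The Statistical methods analyse opioid use, cumulated over the first two postoperative days, as "log-transformed opioid consumption using linear regression and adjusting for age". The rule for zeros is: "If a patient did not receive opioids (amount = 0), 0.5 mg was added in order to facilitate the log-transformation". This states a purpose but no reason for the value 0.5. No other constant, and no model that avoids a constant, is described.

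The outcome is secondary. The Outcome Measures section introduces it with "Additional outcomes included daily opioid use". It still carries a formal claim: the margin is "a ratio of means of 1.2 for the cumulative log-transformed opioid consumption", the test is made "using a 1-tailed noninferiority t-test at the 0.025 significance level", and "If noninferiority was found, superiority would be tested in the same direction".

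The Post-operative Procedures give the natural scale of the amounts: patients leave with "a prescription for oxycodone 5 mg tablets prior to discharge".

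**The concern.** A substituted zero is an arbitrary point on the log scale. If the smallest real amount is one 5 mg tablet, 0.5 mg puts a non-user ln(5/0.5) = 2.30 log units below a one-tablet user. The whole noninferiority margin is ln 1.2 = 0.182, so one step from non-user to one tablet is 12.6 times the margin.

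Two things follow if there are zero users. The zeros widen the spread of log consumption and so the standard error. Any difference in zero users between arms also moves the estimated ratio by an amount that the constant sets. At stake is whether the trial may state noninferiority, and then superiority, on opioid use, when a reader cannot tell whether that statement would survive another reasonable constant.

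**Working it through.** **The plan's own figure.** None is given for the opioid test. The only stated figure is 70 patients for average pain: n per arm = 2 × 2.2² × (1.960 + 1.282)² / (1.25 + 0.5)² = 33.2, so 34 by the normal approximation. With the t distribution, power is 89.8% at 34 per arm and 90.7% at 35, so 70 reproduces. It does not depend on the zero rule.

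**Inputs from the documents.** Constant 0.5 mg, margin ratio 1.2, one-sided 0.025, 35 per arm, 5 mg tablets.

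**Assumed, because the documents give no values.** Share of zero users 5, 10 or 20%; users' arithmetic mean 20 mg; log SD 0.7; amounts rounded to 5 mg tablets (minimum 5).

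**Step 1: shift in the estimate.** For an unadjusted comparison with 35 analysed per arm and k more zero users in one arm, replacing 0.5 mg by c changes the log ratio by (k/35) × ln(c/0.5). For k = 3:

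| c | shift | share of margin | k that moves the estimate by the whole margin |
|---|---|---|---|
| 1 mg | 0.059 | 33% | 9.2 |
| 2.5 mg | 0.138 | 76% | 4.0 |
| 5 mg | 0.197 | 108% | 2.8 |

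With the same true zero share of 5/10/20% in both arms, two Binomial(35, p) counts differ by 3 or more in 16/31/45% of trials.

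**Step 2: equal zero shares.** Percentage of trials that show noninferiority (40,000 simulated trials per scenario, t limits with 68 df, no age term):

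| Users' true ratio | Zeros per arm | 0.5 mg | 1 mg | 2.5 mg | 5 mg |
|---|---|---|---|---|---|
| 1 | 0% | 19.3 | 19.3 | 19.3 | 19.3 |
| 1 | 5% | 12.0 | 13.5 | 16.0 | 18.0 |
| 1 | 10% | 9.2 | 10.7 | 13.8 | 17.0 |
| 1 | 20% | 7.2 | 8.6 | 11.8 | 16.2 |
| 1/1.5 | 0% | 93 | 93 | 93 | 93 |
| 1/1.5 | 5% | 64 | 73 | 84 | 89 |
| 1/1.5 | 10% | 46 | 58 | 75 | 86 |
| 1/1.5 | 20% | 29 | 39 | 60 | 79 |

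- With 0.5 mg at equal use, the mean standard error rises from 0.166 with no zeros to 0.239/0.291/0.360 at 5/10/20%.
- At a users' ratio of 1.20, 0.5 mg claims noninferiority in 2.6/2.7/3.0% of trials and 5 mg in 2.9/3.1/3.8%. Type I error is therefore near 2.5%.
- At equal use and 10% zeros, replacing 0.5 by 1, 2.5 or 5 mg reverses 1.9, 6.0 or 10.5% of decisions. Of these, 1.7, 5.3 and 9.1 points are claims that 0.5 mg misses.
- Range for the 5 mg reversals at 10% zeros: 14.4% to 9.0% as the log SD goes from 0.5 to 0.9, and 10.5% to 7.1% as the users' mean goes from 20 to 40 mg.

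**Step 3: unequal zero shares.** The users' geometric mean is 20 × exp(−0.7²/2) = 15.65 mg (rounding ignored). With 20% zeros on suture, 10% on traditional and equal use among users, the expected log ratio is −0.10 × ln(15.65/c). This is −0.344 (ratio 0.71) with 0.5 mg and −0.114 (ratio 0.89) with 5 mg. Percentage of trials that show noninferiority:

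| Users' true ratio | Zeros, suture v traditional | 0.5 mg | 5 mg |
|---|---|---|---|
| 1 | 20% v 10% | 35 | 36 |
| 1 | 30% v 10% | 68 | 60 |
| 1/1.5 | 20% v 10% | 75 | 94 |
| 1/1.5 | 30% v 10% | 92 | 98 |

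Now let the true ratio of mean amounts sit exactly at 1.2, with 20% v 10% zeros. The users' ratio must then be 1.2 × 0.9/0.8 = 1.35. The expected log ratio is 0.8 × ln 1.35 − 0.10 × ln(15.65/c). That is 0.240 − 0.344 = −0.104 (ratio 0.90) with 0.5 mg, and 0.240 − 0.114 = 0.126 (ratio 1.13) with 5 mg. Noninferiority is then claimed falsely in about 12% of trials with 0.5 mg, against 2.6% for a direct ratio-of-means analysis.

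**Step 4: a model without a constant.** Age-adjusted, 8,000 trials, 10% zeros in both arms, 0.5 mg regression v log-link model with HC3 errors: 8.6% v 13.6% at equal use, 44.0% v 73.2% at a ratio of 1/1.5, and 2.9% v 2.7% at a ratio of 1.20.

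**The case against.** The strongest case against the point has five parts.

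- **There may be no zero users.** Then the rule does nothing. This stands, and only a count by arm can settle it.
- **The test is weak anyway.** At equal use and with no zeros, power is about 19% under these assumptions; with a users' geometric mean of 20 mg and a log SD of 0.5 to 1.0 it is 33% down to 11%. The plan claims 90% power only for average pain. This stands, and the 0.5 mg rule is not the main cause of low power at equal use. The argument is weaker if the suture method lowers use, where 93% falls to 46% at 10% zeros.
- **That benefit scenario is one-sided.** It lowers users' intake but holds the zero shares equal, although a method that reduces need might also produce more non-users. This stands. A reader might infer that the rule simply costs power, or that it favours a false claim. The documents support neither as a general statement, because they give no zero shares and step 3 shows both directions.
- **The margin may be meant on the geometric-mean scale.** The wording joins a ratio of means to a log-transformed amount, so the 12% figure is false noninferiority only on the arithmetic scale. That is fair. On the geometric scale, however, the estimand itself contains the constant.
- **The constant is disclosed and only a secondary outcome is involved.** Both are true, and they limit the severity.

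A reader might also infer that unit and scope are undefined. The documents do not support this. The rule is stated in mg and the window is the first two days after surgery. The phrase "in oxygen with opioids provided, as needed" belongs to the Intra-operative Procedures, outside that window on a plain reading. What remains open is narrower: recovery-room opioids, and the reference opioid for conversion.

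**Conclusion.** The point holds as a minor one, for one secondary outcome. If zero users exist, an unexplained constant can drive a formal noninferiority decision and the superiority test behind it. With equal zero shares the main effect is a larger standard error and lost power, with type I error near nominal. With unequal shares the constant also moves the estimated ratio, in a direction that the documents cannot settle. It can raise power, lower it, or give false noninferiority on the ratio-of-means scale.

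The power and error figures rest on assumed zero shares, users' mean and log SD. The shift formula needs no assumed spread or mean, but it applies to an unadjusted comparison with 35 analysed per arm, whereas the plan adjusts for age and uses modified intention-to-treat. The primary pain analysis and the sample size of 70 are not touched.

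**What to change.** Keep the 0.5 mg log regression as the stated analysis. Then:

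1. Report the number of zero users in each arm.
2. Repeat the regression with at least one larger constant, such as 2.5 or 5 mg.
3. Fit one age-adjusted log-link (Poisson-type) model of cumulative mg with small-sample robust (HC3-type) standard errors. It needs no constant and estimates the ratio of means directly.
4. Label these as sensitivity analyses, and as post hoc if they are added after the data were seen.
5. Qualify the opioid noninferiority or superiority conclusion if it changes across these analyses.

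The cost is one line of counts and a few model runs on existing data. The downsides are several results for one secondary outcome, which need clear labels, and a log-link estimand that is more sensitive to heavy users. No constant is put forward as the right one: 5 mg treats a non-user like a one-tablet user and is slightly liberal with many zeros (3.8% at 20% zeros in step 2).

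### Dislodgement was planned as a noninferiority outcome, but once no suture-group event was seen it was switched to Fisher's exact test, with no risk-difference interval named although one can still be computed

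*Combined protocol and SAP*

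**What the plan says.** The Outcome Measures section of the combined protocol and SAP lists complete catheter dislodgement as a binary additional outcome. Statistical methods gives the intention for it: "We originally planned to estimate the effect of the treatment on the side effect of complete catheter dislodgment as a secondary outcome for testing noninferiority". It then gives the change and the reason: "However, we observed no event in the suture method group. Therefore, we simply compared the groups using Fisher's exact test". The remaining binary outcomes are treated in the same way: "We also compared the randomized groups on binary outcomes using chi-square or Fisher's exact test, as appropriate". No effect estimate or confidence interval is named for dislodgement or for any other binary outcome.

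The noninferiority rule stands earlier in the same section: "Noninferiority was claimed if the upper 95% confidence limit for the treatment effect" fell below the margin. The margins given are a "noninferiority delta of 1.25 for each pain score outcome and a ratio of means of 1.2 for the cumulative log-transformed opioid consumption". None is given for dislodgement, and the model and effect scale planned for it are not stated.

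**The concern.** A noninferiority question asks how much worse the new catheter could be. Fisher's test asks whether the two event rates differ at all. Only a significant result in favour of the suture catheter answers the first question through the second. Any other P leaves it open.

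The substitution was prompted by the observed data, and the stated reason does not require it. Zero events in one arm can break a logistic or ratio model, but not an interval for a difference in proportions.

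The trial compares two catheter designs, and complete dislodgement measures catheter performance directly. With few comparator events, a reader who is given only the P value has no bound on excess dislodgement, although the same data supply one.

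**Working it through.** **Inputs from the documents.** Zero dislodgements in the suture group (Statistical methods); planned size 70, or 35 per group (Sample size and power estimation).

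**Assumptions.** 35 analysed per arm. The comparator count x is not given, so it is ranged over 0 to 6.

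**The plan's own figure.** With margin 1.25, SD 2.2, a true difference of 0.5 favouring suture, one-sided 0.025 and 90% power, n per arm = 2 × 2.2² × (1.960 + 1.282)² / (1.25 + 0.5)² = 33.2, rounded up to 34. The noncentral t gives power 0.898 at 34 and 0.907 at 35, so 35 per arm reproduces. It serves here only as the assumed arm size. The documents give no figure for the dislodgement analysis beyond the zero.

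**Fisher's exact test.** With equal arms and one arm at zero, for x ≥ 1 the two-sided P is 2 × C(35,x)/C(70,x).
- x = 5: 2 × 324,632/12,103,014 = 0.0536.
- x = 6: 2 × 1,623,160/131,115,985 = 0.0248.

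**Newcombe upper limit.** U = d + √[(u₁ − p₁)² + (p₂ − l₂)²], where d = p₁ − p₂ (suture minus traditional), u₁ is the Wilson upper limit for suture and l₂ the Wilson lower limit for the comparator. For 0/35, u₁ = 3.8415/(35 + 3.8415) = 0.0989. For x = 3, p₂ = 0.0857 and l₂ = 0.0296, so U = −0.0857 + √(0.0989² + 0.0561²) = +0.0280.

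**Miettinen-Nurminen upper limit.** Solve for the difference at which the score statistic, with constrained estimates and variance factor 70/69, equals −1.96. At x = 0 this has a closed form: k = 3.8415 × 2/69 = 0.1113, and the limit is k/(1 + k) = 0.1002. The other values were found by root-solving.

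| Comparator events (of 35) | Fisher two-sided P | Miettinen-Nurminen upper limit (points) | Newcombe upper limit (points) |
|---|---|---|---|
| 0 | 1.00 | +10.0 | +9.9 |
| 1 | 1.00 | +7.3 | +7.3 |
| 2 | 0.49 | +4.6 | +5.0 |
| 3 | 0.24 | +1.9 | +2.8 |
| 4 | 0.11 | −0.8 | +0.6 |
| 5 | 0.054 | −3.6 | −1.5 |
| 6 | 0.025 | −6.3 | −3.7 |

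A score-ordered exact unconditional interval agrees closely. Its upper limit lies between +10 and +11 points at x = 0, between +2 and +3 at x = 3, and between −1 and 0 at x = 4.

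**Reading the table.**
- At 0 and 1 events P is 1.00 in both rows, yet the bounds differ by nearly 3 points and neither is close to zero.
- At 3 events P is 0.24, yet an excess of 3 points or more is excluded by both closed-form and score limits.
- At 4 events the exclusion of any excess depends on the method.
- At 5 events both tabulated intervals exclude any excess while P is 0.054.

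**Sensitivity to arm sizes.** With 36 suture and 34 traditional patients, Fisher is already significant at 5/34 (P = 0.023). With 34 and 36 it becomes so at 6/36 (P = 0.025).

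**The case against.** The change is openly disclosed, and the text does not claim noninferiority from Fisher's test; it says only that the groups were compared. The upper-limit rule is written for the primary outcome and continuous secondary outcomes, so carrying it over to a binary outcome is an extension. The section also calls for imbalanced baseline variables to be adjusted for as appropriate, and age was imbalanced. A zero cell can make an age-adjusted logistic or ratio estimate unusable, and an exact test is a common fallback. With no suture events the observed difference cannot favour the comparator, and the worst bound, about +10 points, needs zero events in both arms. If no margin ever existed, the gain is a descriptive interval. If the counts are published, a reader can compute it.

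Most of this stands as a limit on weight. The outcome is secondary, the intervals are scenarios, and the risk-difference interval is unadjusted and may be on a different scale from the planned model. The documents' silence also cannot show that counts or an interval went unreported. It does not remove the point. Disclosing a change does not supply the missing estimate, and difficulty with one model is no reason to give up estimation. Zero suture events does not settle noninferiority either: the exact 95% upper limit for 0/35 alone is 1 − 0.025^(1/35) = 10.0%. The absent margin, scale and model add to what needs to be stated.

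**Conclusion.** The concern holds. A planned noninferiority assessment was replaced, after the data were seen, by a test that cannot make that assessment unless it is significant in favour of suture. No interval is named, although one is available for every comparator count examined.

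The loss depends on that unknown count. With 35 per arm, 0 to 5 comparator events leave Fisher's P above 0.05 while the upper limit runs from about +10 points to below zero. From 6 events Fisher's result already implies noninferiority and little is lost. That threshold shifts slightly with the analysed arm sizes, which are also not given. Whether a dislodgement margin was ever fixed cannot be told from the documents, so the interval by itself supports no formal noninferiority conclusion. This should be changed, but it affects a secondary outcome only.

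**What to change.** - Report the dislodgement count and denominator in each group, and the risk difference (suture minus traditional) with a two-sided 95% Miettinen-Nurminen or exact unconditional interval. Name one method, since the methods can disagree at the boundary.
- State the model, effect scale and noninferiority margin originally planned for dislodgement, or state that no margin was set.
- If a margin was fixed in advance on the risk-difference scale, compare the upper limit with it under the rule used for the other noninferiority outcomes. If not, present the interval as descriptive, set no margin now, and make no noninferiority claim.
- Label the change of method as data-driven and keep Fisher's P as a supplement.
- Note that the interval is unadjusted for age and may be on a different scale from the planned model.

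The cost is a few lines of text and a standard SAS risk-difference option. No new data are needed.
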